## **8.4 Reporting Procedures – Notifying the IRB**

### **8.4.1**

#### **Adverse Event Reporting**

All AEs will be recorded in AE CRFs by a member of the study team only if they are related to the study drug. AEs will be recorded within 3 business days of the study team being made aware of the AE. The relationship of the AE to the study drug will be noted by the PI. AEs that are deemed definitely related or probably related to the study drug will be reported to the IRB within 3 days of their designation as such. AEs that are deemed unrelated or not likely related to the study drug will be recorded on CRFs as described above and will be reviewed at quarterly safety review meetings with the Safety Monitor, and at annual review by the IRB.

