### 8.2.2

### Relationship to Study Agent

The clinician's assessment of an AE's relationship to study drug is part of the documentation process, but it is not a factor in determining what is or is not reported in the study. If there is any doubt as to whether a clinical observation is an AE, the event should be reported. All AEs must have their relationship to study agent assessed. In a clinical trial, the study product must always be suspect. To help assess, the following guidelines are used.

- **Related** – The AE is known to occur with the study agent, there is a reasonable possibility that the study agent caused the AE, or there is a temporal relationship between the study agent and event. Reasonable possibility means that there is evidence to suggest a causal relationship between the study agent and the AE.
- **Not Related** – There is not a reasonable possibility that the administration of the study agent caused the event, there is no temporal relationship between the study agent and event onset, or an alternate etiology has been established.

For all collected AEs, the clinician who examines and evaluates the participant will determine the AE's causality based on temporal relationship and his/her clinical judgment. The degree of certainty about causality will be graded using the categories below.

- **Definitely Related** – There is clear evidence to suggest a causal relationship, and other possible contributing factors can be ruled out. The clinical event, including an abnormal laboratory test result, occurs in a plausible time relationship to drug administration and cannot be explained by concurrent disease or other drugs or chemicals. The response to withdrawal of the drug (dechallenge) should be clinically plausible. The event must be pharmacologically or phenomenologically definitive, with use of a satisfactory rechallenge procedure if necessary.
- **Probably Related** – There is evidence to suggest a causal relationship, and the influence of other factors is unlikely. The clinical event, including an abnormal laboratory test result, occurs within a reasonable time after administration of the drug, is unlikely to be attributed to concurrent disease

CONFIDENTIAL

This material is the property of the NYU School of Medicine and Langone Medical Center. Do not disclose or use except as authorized in writing by the study sponsor

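### Section 8.4.1 contradicts itself on whether non-serious adverse events judged unrelated to the study drug are recorded on the CRF

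*Combined protocol and SAP*

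**What the plan says.** Section 8.4.1 is one paragraph. It opens with "All AEs will be recorded in AE CRFs by a member of the study team only if they are related to the study drug". Two sentences on timing and attribution follow: "AEs will be recorded within 3 business days of the study team being made aware of the AE" and "The relationship of the AE to the study drug will be noted by the PI". It then sets reporting routes. For the stronger causality grades, "AEs that are deemed definitely related or probably related to the study drug will be reported to the IRB within 3 days" of being so classified. For the weaker grades, "AEs that are deemed unrelated or not likely related to the study drug will be recorded on CRFs as described above", and these events "will be reviewed at quarterly safety review meetings with the Safety Monitor, and at annual review by the IRB".

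Other sections bear on the same question:

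- **8.2.2 (Relationship to Study Agent)** says of the clinician's causality assessment that "it is not a factor in determining what is or is not reported in the study". It then sets out a causality scale that runs down to not related, introduced by "For all collected AEs, the clinician who examines and evaluates the participant will determine" causality.
- **8.3 (Time Period and Frequency)** has all AEs that are not SAEs captured on a form, and requires every on-study AE to be documented whatever its relationship to the drug.
- **8.4.2 (Serious Adverse Event Reporting)** puts all SAEs on SAE CRFs, with no relatedness condition.
- **10.4.4 (Safety Analyses)** says the PI will ascertain and report all AEs.
- **Section 11** makes the CRF the study's main instrument for data collection.

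**The concern.** A recording rule should not depend on a judgement that the recorded data are later used to test. Under the opening sentence of 8.4.1, the view that a non-serious event is unrelated decides whether it enters the AE CRF at all. The study is open-label (4.1), so that view is formed knowing that the patient takes Envarsus XR. There is no DSMB; oversight beyond the PI rests on one Safety Monitor who meets the PI at least quarterly (8.6).

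At stake is the completeness of the non-serious AE record. Events dismissed one at a time as unrelated can form a pattern across participants, and reviewing them together is the purpose of the quarterly meeting. Events that were never entered on the AE CRF cannot be brought to that meeting from it.

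**Working it through.** The point is textual. The plan states no figure on it, so there is nothing to reproduce or recompute. The check sets the sentences side by side.

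1. **Scope.** SAEs have their own recording rule in 8.4.2, without a filter. The conflict in 8.4.1 therefore matters for non-serious AEs only.

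2. **Test case.** Take a non-serious AE judged not related. The opening sentence keeps it off the AE CRF. The closing sentence puts it on a CRF and sends it to quarterly and annual review. A coordinator cannot do both.

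3. **Can the closing sentence's back-reference reconcile them?** It says these events are recorded in the manner already described. There are two readings.
   - If the reference is to who records and how fast, the filter and the closing sentence still collide.
   - If the reference carries the filter forward, no unrelated AE is ever on a CRF. The sentence then requires nothing, and the two reviews have no CRF entries to look at.

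   Neither reading removes the conflict.

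4. **Could two different forms be meant?** The only CRFs described earlier in 8.4.1 are the AE CRFs of its opening sentence. The paragraph gives no second form to which the closing sentence could refer.

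5. **Which sentence is the outlier?** The other sections side with recording regardless of relatedness, with differing weight:
   - 8.3 is the strongest. It asks for form capture of non-serious AEs and for documentation whatever the relationship. It calls the form an RF; reading this as CRF is likely but is an inference.
   - 8.2.2 says relatedness does not decide what is reported, and it grades every collected AE on a scale that includes not related. It does not mention a CRF.
   - 10.4.4 promises all AEs. It does not mention a CRF either.
   - 8.4.2 opens with the same structure as 8.4.1 but without the condition.
   - The second and third sentences of 8.4.1 fit recording of all AEs, because the clock starts at awareness of any AE and the relationship is then noted. They recur almost unchanged in 8.4.2, so they add little.

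   The conflict inside 8.4.1 is enough for the finding. The other sections indicate which clause to remove.

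6. **Size.** The prospective cohort is 40 patients, each followed for one year. The documents give no rate of non-serious AEs and no expected share judged unrelated, so no event count can be derived.

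**The case against.** The strongest reply is that the restriction may be deliberate. The opening of 8.4.2 is the same sentence for SAEs without the condition, so someone may have added the condition to 8.4.1 on purpose and left the closing sentence unrevised. 8.3 also has the PI record reportable events, a qualifier it does not define. And AEs are defined broadly in 8.1.1, to include intercurrent illness and abnormal results that lead to further tests, while 7.2.1 has weekly laboratory work for three months. Recording everything in lung transplant recipients could be a real burden.

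Part of this stands. The sponsor's intent cannot be proved from the text, and the burden is unknown. But a deliberate restriction would leave four places wrong: the closing sentence of 8.4.1, 8.2.2, 8.3 and 10.4.4. The text needs correction under either intent.

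The harm is also limited. Section 14.1 has clinical data, AEs included, collected in subject binders and clinical data entered in REDCap. A reader might infer that unrelated events would leave no trace anywhere in the study records. The documents do not support that: the exposure is absence from the AE CRFs, and so from reviews and summaries built on them.

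A reader might also infer a second contradiction, that AEs judged possibly related have no reporting route. 8.4.1 indeed names none for them. But 8.1.3 and 8.4.3 send possibly related events that meet the unanticipated-problem criteria to the IRB within 3 days and require the Safety Monitor to be notified. The 3-day rule in 8.4.1 may also reach related SAEs. What is left is missing detail, not a contradiction, and it forms no part of this point.

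**Conclusion.** The contradiction is real and the paragraph cannot be followed as written. For non-serious AEs judged unrelated or not likely related, 8.4.1 both excludes and requires CRF recording. Its opening sentence also disagrees with 8.2.2 and 8.3.

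The consequence is conditional on staff applying the opening sentence. In that case the quarterly Safety Monitor review, the annual IRB review of these events, and the full AE report in 10.4.4 could not be produced from the AE CRFs.

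A reader might go further and infer that the trial's safety data as a whole, or its main result, are compromised. The documents do not support that. All SAEs are recorded under 8.4.2 and go to the sponsor under 8.5. The named safety endpoints are worsening kidney disease and discontinuation of therapy; creatinine is collected routinely under 7.2.1. The primary endpoint is the percentage remaining on Envarsus XR at one year. None of these depends on the disputed clause.

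The choice of which clause to remove assumes that recording of all AEs was intended. The surrounding sections favour that reading but do not prove it. The correction should be made, and it is small.

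**What to change.** Reconcile 8.4.1 to one recording rule: end its opening sentence after the words on who records the event, and delete the condition that the event be related to the study drug. Relatedness then affects only the reporting route and timing, which the rest of the paragraph already sets out.

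The edit is one clause. The ongoing cost is additional AE CRF entry, which the documents do not allow to be estimated; the closing sentence of 8.4.1 already calls for it.

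If the sponsor did intend to record related events only, the opening sentence can stay, but the closing sentence of 8.4.1, 8.2.2, 8.3 and 10.4.4 must all be changed to match. That is the larger edit, and it would give up the quarterly and annual review of unrelated non-serious events.

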### **8.4.2**

#### **Serious Adverse Event Reporting**

All SAEs will be recorded in SAE CRFs by a member of the study team. SAEs will be recorded within 3 business days of the study team being made aware of the SAE. The relationship of the SAE to the study drug will be noted by the PI. SAEs that are both unexpected and deemed related to the study drug will be reported to the IRB and the Safety Monitor within 24 hours of the PI designation as such. The Safety Monitor will determine the need for an emergency meeting between the Safety Monitor and the study team (see safety oversight below) or whether these can be reviewed at quarterly meetings. SAEs that are deemed unrelated or not likely related to the study drug will be recorded on CRFs, will be reported to IRB and Safety Monitor within 3 days of their designation as such and will be reviewed at quarterly safety meetings.

### **8.4.3**

#### **Unanticipated Problem Reporting**

Incidents or events that meet the OHRP criteria for UPs require the creation and completion of an UP report form. It is the PI's responsibility to report UPs to their IRB and notify the Safety Monitor. The UP report will include the following information:

- Protocol identifying information: protocol title and number, PI's name, and the IRB project number;
- A detailed description of the event, incident, experience, or outcome;
- An explanation of the basis for determining that the event, incident, experience, or outcome represents an UP;
- A description of any changes to the protocol or other corrective actions that have been taken or are proposed in response to the UP.

To satisfy the requirement for prompt reporting, UPs will be reported using the following timeline:

- UPs that are SAEs will be reported to the IRB within 3 days the investigator becoming aware of the event.
- Any other UP will be reported to the IRB within 3 days of the investigator becoming aware of the problem.

### **8.4.4**

#### **Reporting of Pregnancy**

If any pregnancy occurs in a study subject, the PI will be notified immediately and the IRB will be notified within 3 days of discovery of the pregnancy. Data regarding safety of tacrolimus in pregnant women suggests an increased risk of premature delivery and potential for fetal harm. Standard of care medications utilized for lung transplant recipients have known contraindications in pregnancies therefore any pregnancies will need to be managed as per standard of care with the lung transplant team. Counseling of pregnant subjects with regard to the risks of continuing versus discontinuing Envarsus XR will occur with patients once counseling with regard to the contraindications of the standard of care transplant medications has occurred.

## **8.5 Reporting Procedures – Notifying the Study Sponsor**

CONFIDENTIAL

This material is the property of the NYU School of Medicine and Langone Medical Center. Do not disclose or use except as authorized in writing by the study sponsor

The study clinician will complete a SAE Form within the following timelines:

- All deaths and immediately life-threatening events, whether related or unrelated, will be recorded on the SAE Form and submitted to the study sponsor within 24 hours of site awareness. See Section 1, Key Roles for contact information.
- Other SAEs regardless of relationship will be submitted to the study sponsor within 72 hours of site awareness.

All SAEs will be followed until satisfactory resolution or until the site investigator deems the event to be chronic or the adherence to be stable. Other supporting documentation of the event may be requested by the study sponsor and should be provided as soon as possible.

As a follow-up to the initial report, within the following 48 hours of awareness of the event, the investigator shall provide further information, as applicable, on the unanticipated event or the unanticipated problem in the form of a written narrative. This should include a copy of the completed Unanticipated Problem form, and any other diagnostic information that will assist the understanding of the event. Significant new information on ongoing unanticipated adverse effects shall be provided promptly to the study sponsor.

## **8.6 Safety Oversight**

It is the responsibility of the Principal Investigator to oversee the safety of the study. This safety monitoring will include careful assessment and appropriate reporting of adverse events as noted above, as well as the construction and implementation of a site data and safety-monitoring plan. Medical monitoring will include a regular assessment of the number and type of serious adverse events.

The study will not have a formal DSMB as there are no anticipated SAE from routine testing and monitoring post-lung transplant, along with the off-label use of an approved FDA medication (Envarsus XR) for prevention of acute rejection following lung transplant and with the recommended dosing. Additionally, this trial will not be looking for a new indication or use of Envarsus XR.

Safety oversight will be under the direction of the PI and a Safety Monitor with expertise in transplantation ([name] – Transplant Cardiology). This individual will be involved as a consultant but not as an investigator of the trial and will provide an independent evaluation of each one of the SAE related to the treatment with Envarsus XR. Furthermore, the PI and the Safety Monitor will meet at least quarterly to discuss patient progress and any relevant study related events that meet criteria for routine review. The Safety Monitor will review de-identified data only.

## **9 Clinical Monitoring**

Clinical site monitoring is conducted to ensure that the rights and well-being of human subjects are protected, that the reported trial data are accurate, complete, and verifiable, and that the conduct of the trial is in compliance with the currently approved protocol/amendment(s), with GCP, and with applicable regulatory requirement(s).

## **10 Statistical Considerations**

### **10.1 Statistical and Analytical Plans (SAP)**

No formal SAP is required as the study will employ only a single prospective arm with comparison to a historical control.

CONFIDENTIAL

This material is the property of the NYU School of Medicine and Langone Medical Center. Do not disclose or use except as authorized in writing by the study sponsor

## **10.2 Statistical Hypotheses**

We hypothesize that freedom from ACR within the first year post-lung transplant will be reduced by early and continued prescription of Envarsus XR as compared to IR tacrolimus. Additionally, we hypothesize that key related immunologic outcomes, de novo DSA and CLAD, may be reduced due to less frequent rejection.

## **10.3 Analysis Datasets**

All subjects will be entered into a database containing de-identified information. All patients who take one dose of the study drug will be included in the safety analyses (intention-to-treat). However, only patients completing the full first year post-lung transplant will be included in the efficacy analysis (per-protocol analysis).

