### 3.2 Secondary Objectives (if applicable)

Secondary objectives will be to assess immunologic outcomes that may be impacted by conversion to Envarsus XR and potential mitigation of concentration-related side effects.

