## **6.2 Study Agent Accountability Procedures**

The Investigational Pharmacist must complete the study drug accountability record. Any deviations or discrepancies must be reported to the PI immediately. The PI or co-investigator will review drug accountability during routine monitoring visits.

The accountability records will contain complete records of receipt, storage, dispensation and return for all used and unused tablets of Envarsus XR. Documentation will include batch numbers, expiry dates, and quantities received/dispensed/returned/destroyed. The accountability records and the study drug must be reconciled and discrepancies between the amount received, dispensed and returned/destroyed drug must be accounted for. This is applicable for unused, used and partially used and deliberately or accidentally damaged tablets of study drug.

Unused or damaged study drug must be kept at the Investigational Pharmacy until study closure and then returned to Veloxis Pharmaceuticals unless otherwise agreed upon with Veloxis Pharmaceuticals. Used study drug will be destroyed by the Investigational Pharmacist according to local guidelines after reviewed by the PI and confirmed by Veloxis Pharmaceuticals.

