### **7.2.2** **Control Cohort**

### **Retrospective data to be collected in the Historical**

Specific data pertaining to primary and secondary outcomes to be collected in the Historical Control Cohort is the same as listed above in the Prospective Cohort and at the same time points.

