## 8.3 Time Period and Frequency for Event Assessment and Follow-Up

The occurrence of an AE or SAE may come to the attention of study personnel during study visits and interviews of a study participant presenting for medical care, or upon review by a study monitor. All AEs including local and systemic reactions not meeting the criteria for SAEs will be captured on the appropriate RF. Information to be collected includes event description, time of onset, clinician's assessment of severity, relationship to study product (assessed only by those with the training and authority to make a diagnosis), and time of resolution/stabilization of the event. All AEs occurring while on study must be documented appropriately regardless of relationship. All AEs will be followed to adequate resolution.

Any medical condition that is present at the time that the participant is screened will be considered as baseline and not reported as an AE. However, if the study participant's condition deteriorates at any time during the study, it will be recorded as an AE. UPs will be recorded in the data collection system throughout the study.

Changes in the severity of an AE will be documented to allow an assessment of the duration of the event at each level of severity to be performed. AEs characterized as intermittent require documentation of onset and duration of each episode.

The PI will record all reportable events with start dates occurring any time after informed consent is obtained until 7 (for non-serious AEs) or 30 days (for SAEs) after the last day of study participation. At each study visit, the investigator will inquire about the occurrence of AE/SAEs since the last visit. Events will be followed for outcome information until resolution or stabilization.

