### **10.4.4**

#### **Safety Analyses**

Safety endpoints include worsening chronic kidney disease and discontinuation of therapy will be analyzed as changes from baselines and summary data during the course of treatment, respectively. These will be compared as linear regression and frequencies using the chi-square test, respectively. All AEs will be ascertained and reported by the PI.

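### The safety set holds no historical controls, the discontinuation test is run against 0/20 by selection, and side effects have no like-for-like comparator

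*Combined protocol and SAP*

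**What the plan says.** **Safety set.** Section 10.3: "All patients who take one dose of the study drug will be included in the safety analyses (intention-to-treat". It gives no matching rule for the historical cohort. The study drug is Envarsus XR; in 6.2, for example, "The accountability records will contain complete records of receipt, storage, dispensation and return for all used and unused tablets of Envarsus XR".

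**Safety analyses.** Section 10.4.4 names two safety endpoints, worsening chronic kidney disease (CKD) and discontinuation of therapy, and adds: "These will be compared as linear regression and frequencies using the chi-square test, respectively". For AEs it says only that the PI will ascertain and report them.

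**Controls.** Section 5.1 admits a historical control only if the patient completed a year from transplant on IR tacrolimus. Section 7.2.2 sets what is extracted for them: "Specific data pertaining to primary and secondary outcomes to be collected in the Historical Control Cohort is the same as listed above". The lists in 7.1.2 and 7.2.1 cover biopsy grade, augmented immunosuppression, FEV1, DSA, WBC, potassium, creatinine and tacrolimus trough. They contain no AE or symptom item.

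**AEs in the prospective arm.** Section 8.3: "At each study visit, the investigator will inquire about the occurrence of AE/SAEs since the last visit". It also says "All AEs occurring while on study must be documented appropriately regardless of relationship", whereas 8.4.1 says "All AEs will be recorded in AE CRFs by a member of the study team only if they are related to the study drug".

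**Objective.** Section 3.2 includes "potential mitigation of concentration-related side effects" among the secondary objectives. Section 4.2.2 gives no endpoint for it.

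**The concern.** A regression or chi-square comparison needs two groups, and 10.4.1 describes the study as two-arm, with the historical cohort as comparator. The set defined for safety has only one of those groups. An analyst must either run no comparison or choose a control set that the protocol never defined. No separate SAP will settle the choice, because 10.1 says none is required.

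Three things are at stake. The renal comparison is one that both cohorts' data can support, and the Protocol Summary lists the effect of formulation on CKD as an objective. The discontinuation comparison could produce a significant result that reflects only how controls were chosen. The side-effect objective speaks of mitigation, which invites a comparison with IR tacrolimus that the data collection does not support.

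**Working it through.** The documents give no power, event rate or effect size for safety, so there is no stated figure to reproduce. The sizes are 40 Envarsus XR and 20 IR tacrolimus patients (Protocol Summary), and the test level is two-sided 0.05 (10.4.1).

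**1. Who is in the safety set.** The rule is at least one dose of Envarsus XR. Controls spent their qualifying year on IR tacrolimus. As written the set holds up to 40 patients on one side and 0 on the other.

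**2. Whether control renal data are missing.** They are not. Creatinine is listed in 7.2.1 (weekly for three months, then monthly), and 7.2.2 carries that list to the controls at the same time points. Change in eGFR is a secondary endpoint (4.2.2), but none of the six analyses in 10.4.3 covers it, so 10.4.4 is the only endpoint-specific renal analysis. The set definition, not missing data, removes the comparator.

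**3. Discontinuation.** Take discontinuation to mean stopping the assigned formulation within the year. Section 5.1 then fixes the control count at 0/20. With x of 40 stopping Envarsus XR, the uncorrected chi-square is

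60 × (20x)² / [40 × 20 × x × (60 − x)] = 30x / (60 − x).

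- x = 6: 180/54 = 3.33, P = 0.068
- x = 7: 210/53 = 3.96, P = 0.047

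The test is therefore significant from 7/40 (17.5%). Fisher's exact test first crosses at 8/40 (P = 0.043) and the continuity-corrected chi-square at 10/40 (P = 0.037).

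The documents give no discontinuation rate, so the true Envarsus XR rate is assumed over a range. The chance of P < 0.05 is the binomial(40, rate) probability of reaching the threshold:

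| Assumed true rate | Uncorrected chi-square (x ≥ 7) | Fisher (x ≥ 8) | Corrected chi-square (x ≥ 10) |
|---|---|---|---|
| 10% | 10% | 4% | 0.5% |
| 15% | 39% | 24% | 7% |
| 20% | 71% | 56% | 27% |
| 25% | 90% | 82% | 56% |

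These figures hold even if unselected IR tacrolimus patients stopped at the same rate, because such patients cannot enter the control cohort.

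**4. AEs and symptoms.** Section 8.3 has the investigator ask at each visit in the prospective arm. The control extraction list has no such item. Sections 10.4.3 and 10.4.4 contain no between-cohort AE test, so there is no planned test whose error rate could be computed.

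**The case against.** The strongest reply is that this is a pilot with a descriptive feasibility endpoint (10.4.2) and no power calculation (10.5), and that the safety-set sentence is loose wording. The control renal data exist, and eGFR change is also a secondary endpoint outside the safety set. That stands in part: the renal fault is one of definition and is easily mended. It still needs mending, because 10.4.4 calls for a comparison that 10.3 does not permit.

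The objective in 3.2 could also be read as within-patient change, since all prospective patients start on IR tacrolimus (2.2.3). That is possible, but no endpoint, analysis or scheduled assessment is given for that reading either.

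Fisher's exact test is allowed where appropriate (10.4.1) and weakens the discontinuation figures. At 7/40 the smallest expected count is 20 × 7/60 = 2.3, so Fisher would be the usual choice. Section 10.4.4 names chi-square, however, and no choice of test repairs a control rate fixed at zero.

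A reader might infer more than the documents support:

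- *That harms in general are not collected for controls.* Creatinine, potassium and WBC are.
- *That unequal AE inquiry spoils the two named safety tests.* Neither CKD nor discontinuation depends on asking about AEs.
- *That AE comparisons are biased against Envarsus XR by a stated amount.* No such comparison is planned. Sections 8.3 and 8.4.1 also conflict on whether unrelated AEs are recorded in the prospective arm, so under-recording there is possible and the direction is unknown.
- *That every scheduled column is an AE interview.* The Schedule of Events has no AE row, and nine of the 22 post-dose columns list laboratory work only.

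**Conclusion.** The point holds in a limited form. The safety set in 10.3 excludes every historical control, while 10.4.4 plans comparisons that need them. For CKD this is a defect of definition.

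The discontinuation test is invalid because control eligibility sets the comparator at 0/20. Significance starts at 7/40, and an assumed true rate of 15-20% yields it in 39-71% of trials with the uncorrected chi-square (24-56% with Fisher) without any difference between formulations. This rests on 40 and 20 patients, on the assumed rates, and on discontinuation meaning a stop of the formulation within the year.

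The side-effect objective has no like-for-like comparator, and no magnitude or direction is attached to that.

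The renal comparison, once its controls are restored, is still not free of bias. It sets any-dose Envarsus XR patients against one-year completers, so IR tacrolimus patients who died or stopped within the year, including for renal reasons, are absent.

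**What to change.** **Section 10.3.** Replace the safety-set sentence with two sets and delete the intention-to-treat label:
- (a) AE/SAE set: all patients with at least one Envarsus XR dose, reported descriptively in that arm only.
- (b) Between-cohort safety set: all dosed Envarsus XR patients and all historical controls, limited to routinely scheduled laboratory measures (creatinine/eGFR, potassium, WBC).

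**Section 10.4.4.**
- Apply between-group tests to set (b) only.
- Report discontinuation descriptively for Envarsus XR, with no chi-square test.
- State that controls are one-year completers and that the renal comparison therefore carries selection bias.
- As a sensitivity analysis, repeat the renal comparison in Envarsus XR patients who also completed one year. This aligns the entry rule but does not remove selection if reasons for stopping differ.

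**Section 3.2.** Make symptom side effects descriptive within the Envarsus XR arm.

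**Sections 8.3 and 8.4.1.** Reconcile the two rules on recording AEs unrelated to study drug.

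**Cost.** Protocol wording and one extra analysis of data already planned; no new visits or data collection. The trial gives up comparative claims on symptomatic side effects and on discontinuation, which its data cannot support. Little is lost on discontinuation, because the primary endpoint already describes the percentage remaining on Envarsus XR at one year.
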